3. OBJECTIVES

3.1 Primary objective

The study will compare the level of thermal care delivered to a clinically stable baby in the mOm incubator and a standard (non-humidified) incubator.

3.2 Secondary objectives

Assessment of:

- Comparability to maintain clinical stability by measurement of physiological parameters.
- The mOm incubators ability to maintain and regulate its temperature to within the appropriate BS standard⁵ in clinical practice.
- Comparison of between subject cleaning times.
- Incubator performance related adverse events.
- Staff feedback on the experience of using the mOm incubator (*i.e.* usability) will also be collected.

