2.1.2 Risks and Management of Risk

The mOm incubator has been carefully designed to maintain a stable temperature environment for the baby.

The mOm infant incubator been manufactured under current Good Manufacturing Practice (GMP), designed and tested to provide a level of thermoregulation that meets the harmonised standards set for conventional baby incubators (BS EN 60601-2-19)^{5,6}. More information and testing results for the mOm incubator will be provided to the site clinical research team in the form of an Investigator Brochure (IB). The clinical research team will have full control and responsibility for the baby's care and can withdraw a subject from the study at any time for any reason. The risks should therefore be no more than for standard routine incubator care.

If for any reason the subject, or incubator, has any unforeseen serious adverse event whilst the baby is in the mOm incubator the subject will immediately be removed from the study and placed into standard care. Monitoring of the serious adverse event will be followed up and if the adverse event is a serious device adverse event, the study will be halted with immediate effect and only be continued when the Sponsor and Chief Investigator are confident that the issue is resolved and will not be repeated.

If there are any concerns about temperature stability (or any other matter) in any baby being nursed in the mOm incubator during the study, then standard protocols for clinical evaluation by a doctor will be followed. At the discretion of the attending clinician, the baby can be moved into a conventional (standard) incubator at any time without restriction. A spare standard incubator will always be available for this purpose.

If there are unexpected clinical incidents such as Serious Adverse Device Events (SADE) these will be reported to the Sponsor, the Research Ethics Committee (REC), Medicines and Healthcare products Regulatory Agency (MHRA), NHS Trust Research and Development as well as through the normal NHS Trust Risk reporting mechanisms (Datix).

Photographs and/or video recordings of the use of the mOm incubator may be taken during the study but will be taken in such a way so that the baby cannot be identified. The study will adhere to the principles outlined in the Declaration of Helsinki⁷, relevant Sponsor's SOPs and study- specific manuals included in the Investigator Site File (ISF) and Trial Master File (TMF), and, will follow the principles of GCP⁸.

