4.2.2 Temperature stability and regulation

Hourly record of temperatures displayed on the incubator:

- the actual incubator temperature
- set temperature of the incubator
- Core/truncal temperature (from vital signs monitor/skin probe)

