6.2 Procedure

There will be two arms to the protocol as detailed in section 5. The Case Report Form labelled with the appropriate subject number contains the data forms for that subject and a randomisation envelope attached inside the cover of the CRF which indicates which incubator type (standard or mOm) will be used for the baby to spend the first 24 hours in, before being switched to the alternate incubator type for a further 24 hours.

All data collected for the duration of the study will be entered in the appropriate source data (e.g. medical notes, electronic data capture systems, cleaning logs etc) and into the subject's CRF. Adverse events (AE) should be entered.

Baseline data such as length, weight, gender, core/truncal temperature (recorded at time point 0 in physiological recordings section), GA at birth, date of birth and current age of the baby will be recorded on entry to the study. Hourly observations (+/- 15 minutes) will be taken throughout the following 48 hours of incubator care, and will include temperature data displayed on the incubator, plus routine clinical observations of the baby (i.e. pulse rate, O₂ saturation and respiration rate), plus axillary temperature as per standard practice and blood pressure recorded at least once per day (See Table 1 below)

Table 1: Clinical Data Recording

Parameter	Frequency
Core/Truncal Temperature	Hourly
Pulse Rate	Hourly
Oxygen Saturation	Hourly
Respiration Rate	Hourly
Axillary Temperature	As per standard of care (usually every 2-4hrs)
Blood Pressure	As per standard of care (at least once per day)
Events (e.g. door open for feeding, care, baby removed for cuddles)	For each event record start and end time, type of activity, number of portholes/door open, any error/alarms on the incubators and any comments.

Each incubator will be individually identified by serial number for reference in CRFs, source documents (medical record/chart) and on cleaning logs. The randomisation details and the identification number of the incubators used will be recorded when the subject put into the first incubator; likewise, at the 24 hours cross-over point.

Further details about the mOm incubator can be found in the Investigator brochure (IB) filed in the ISF. For the incubator, hourly temperature readings from the digital display, time to set up, time to clean, types of cleaning performed and reasons/times when incubator opened to administer to baby's care will be recorded.

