All data will be analysed based on intention-to-treat. Statistical analysis will focus on babies' temperature fluctuations whilst in each of the two incubators. Graphical displays of these, as well as summary statistics such as the variance of temperature throughout the two 24-hour periods will be presented. A 95% confidence interval for the size of these temperature fluctuations for each incubator type will be calculated and this measure will be used to consider whether the mOm incubator works as well as the standard one in maintaining temperature control. Secondary outcome measures will be presented similarly.

Questionnaire data will be summarised to assess usability and acceptability of the mOm incubator to the clinical research team (staff).

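### Incubator readings taken from the display can show stability and set-point tracking, but cannot verify the absolute air-temperature accuracy that a conformity objective implies

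*Combined protocol and SAP*

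**What the plan says.** Section 3.2 lists among the secondary objectives an assessment of the mOm incubator's "ability to maintain and regulate its temperature to within the appropriate BS standard", and places that assessment in clinical practice.

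The matching outcome is section 4.2.2, introduced as "Hourly record of temperatures displayed on the incubator". It has two incubator items, "the actual incubator temperature" and "set temperature of the incubator", and one item that belongs to the baby, the core/truncal temperature, whose source is given as the vital signs monitor or skin probe. Section 6.2 confirms the source of the incubator data: "hourly temperature readings from the digital display". It also asks for the start and end time of each opening or care event, and for any incubator errors or alarms.

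On conformity, section 2.1.2 says the device was "designed and tested to provide a level of thermoregulation that meets the harmonised standards set for conventional baby incubators (BS EN 60601-2-19", and refers to test results in the Investigator Brochure.

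Section 8 gives no analysis specific to this objective. It says only "Secondary outcome measures will be presented similarly", after describing graphs, the variance of temperature over each 24-hour period and a 95% confidence interval for the size of the baby's fluctuations. The documents give no limit taken from the standard and no definition of being within it.

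**The concern.** The objective is worded as a question of conformity with a safety standard, yet the device's own readout is the only direct source on the device's temperature. The documents describe no independent air probe, reference thermometer or in-study check of the display. Close agreement between displayed and set temperature could therefore be reported as meeting the standard in clinical use, although an inaccurate sensor could produce the same agreement.

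The planned analysis adds a second difficulty. If incubator temperature is presented in the same way as the baby's temperature, the summary will be the raw fluctuation of the displayed value. Staff may change the set temperature deliberately, and the display will follow. Raw fluctuation would count that as instability even when the incubator is doing what it was told.

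**Working it through.** **The plan's own figure.** None is given for this objective. The one precision figure in section 8, ±0.33 °C with 36 babies, concerns the baby's temperature fluctuation. It reproduces as 1.96 × 1/√36 = 0.327 if the SD is 1 °C (an assumption; no SD is stated). Nothing below depends on it.

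**Step 1: what the display can carry.** Let S be the set temperature, D the displayed temperature, A the true air temperature and b a constant sensor offset, so A = D + b. Assume the control acts on the same sensor that feeds the display; the documents do not say. Then:

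- recorded: D − S = e, the regulation error
- needed for accuracy: A − S = e + b

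The offset b does not appear in D − S, so neither more babies nor more readings would reveal it there. The SD of A − S equals the SD of D − S for any constant b, so variability around the set point is measured correctly.

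**Step 2: illustration.** Take e as normal with mean 0 and SD σ = 0.3 °C, and a limit of ±L. The share of true values within the limit is Φ((L − b)/σ) − Φ((−L − b)/σ). The displayed share is the same expression with b = 0. The values of σ, L and b are assumptions; none comes from the documents.

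| Limit L (°C) | Displayed, any b | True, b = 0 | b = 0.5 | b = 1.0 | b = 1.5 | b = 2.0 |
|---|---|---|---|---|---|---|
| 0.5 | 90.4% | 90.4% | 50.0% | 4.8% | 0.0% | 0.0% |
| 1.0 | 99.9% | 99.9% | 95.2% | 50.0% | 4.8% | 0.0% |
| 1.5 | 100% | 100% | 100% | 95.2% | 50.0% | 4.8% |

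Worked entry, L = 1.0 and b = 0.5: Φ(0.5/0.3) − Φ(−1.5/0.3) = Φ(1.67) − Φ(−5) = 0.952.

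**Step 3: can the baby's data fill the gap?** Suppose staff adjust the set point until the baby is comfortable at a true air temperature A*. On average S = A* − b, and the within-baby contrast between incubators is

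S(mOm) − S(standard) = [A*(mOm) − A*(standard)] − [b(mOm) − b(standard)].

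The second bracket is the difference in sensor offset. The first is any real difference in the air temperature the baby needs, because of how the incubators are built or because the two 24-hour periods differ. The recorded data do not separate the two brackets. The same holds for a shift in skin or axillary temperature at a fixed set point. A large offset might leave a trace, but could not be identified as an offset.

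**Step 4: raw fluctuation against display-minus-set.** With e independent of S, Var(D) = Var(S) + σ². For one deliberate set-point change of 1.0 °C (assumed) halfway through 24 hourly readings, the 12 readings on each side lie 0.5 °C from the mean, so Var(S) = 0.25. The SD of D is then √(0.25 + 0.09) = √0.34 = 0.58 °C, while the SD of D − S stays at 0.30 °C. Raw fluctuation would almost double without any failure of regulation.

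**The case against.** The strongest reply is that the objective concerns maintaining and regulating temperature, and that displayed and set readings address this directly. That stands. A reader might infer that the objective cannot be answered at all; the documents do not support this. Stability and set-point tracking can be assessed, and only absolute accuracy is out of reach.

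A second reply is that the display is not the only evidence. Skin and axillary temperatures, alarms, openings and incubator serial numbers are also recorded, and each baby is observed in both incubators. This also stands as far as it goes. It would be too strong to say that the whole dataset would look the same for a miscalibrated device: a large offset might shift the baby's temperature or the set point chosen. That evidence is indirect and confounded, so it does not verify accuracy.

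A third reply is that sensor accuracy may be covered by the pre-study testing in the Investigator Brochure, or by study manuals in the site file. That may be so. Neither these nor the text of the standard is available here, so what the standard asks of a displayed temperature cannot be settled. But pre-study testing is not an assessment in clinical practice, which is what section 3.2 promises.

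Finally, no section says that the report will claim conformity, or that the display alone will decide it, and section 8 calls the analysis largely descriptive. The risk arises because the objective is worded as conformity while no other direct incubator-temperature data are collected.

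**Conclusion.** The point holds for absolute accuracy only. The planned readings support a statement about displayed stability and agreement with the set point. They do not support a conclusion that true air temperature met the standard in clinical use. In the illustration with a ±1.0 °C limit, the displayed share stays at 99.9% while the true share runs from 99.9% with no offset to 0.0% with an offset of 2.0 °C. This rests on a constant offset, a sensor error common to control and display, and assumed values for spread and limit.

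A reader might infer that the mOm incubator is inaccurate or fails the standard. Nothing in the documents suggests that; the point is about what the trial can conclude. It is a minor point on one secondary objective. The primary endpoint is the baby's truncal skin temperature and is untouched.

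**What to change.** - **Section 3.2:** reword the objective as stability of the displayed incubator temperature and its agreement with the set temperature in clinical use, for mOm and standard incubators.
- **Section 8:** replace the general sentence, for this outcome, with an analysis of hourly display-minus-set differences per baby and incubator type, rather than raw fluctuation of the displayed temperature. Show readings taken during recorded openings separately, using the start and end times already collected.
- **Sections 3.2 and 8:** state that absolute accuracy and conformity with the standard are not concluded from this trial and rest on the pre-study testing cited in section 2.1.2.

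This needs no new equipment, measurements or babies. The cost is protocol and analysis wording and a slightly narrower secondary claim. If the sponsor prefers to keep a conformity objective, wording alone will not do. The plan would need an independent calibrated air-temperature reading or a documented display check, together with the limits of the standard that apply and the rule for judging readings against them.

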4. OUTCOME MEASURES

4.1 Primary Outcome Measure

Thermo-regulation ability of incubator to maintain stable core skin temperature of the baby over 24 hours.

4.2 Secondary Outcome Measures

4.2.1 Clinical stability:

- Pulse rate (Hourly)
- Respiratory rate (Hourly)
- Oxygen saturation (Hourly)
- Blood pressure (As per standard of care or at least once per day)
- Axillary Temperature (As per standard of care, usually every 2-4 hours)

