7. ADVERSE EVENTS

7.1 Adverse event (AE)

Any undesirable clinical occurrence in a subject, whether considered to be procedure related or not, that includes a clinical sign or symptom. Typical AEs which should be recorded include but are not limited to: skin injury or infection, pressure sores, hyperthermia, hypothermia, apnea and bradycardia. AEs also include Adverse Device Events (ADEs). ADEs are any undesirable device related event, whether clinically relevant to the subject or not. Typical device ADEs which should be recorded include but are not limited to: rainout, practical access issues, degradation of part of the incubator, inadvertent displacement of lines thought to be due to the design of the incubator.

AEs will be recorded from the time the subject has been enrolled and placed in the first incubator type until the end of their participation in the study (*i.e.* after 48 hours incubation is complete), unless a device related adverse event is on-going in which case it will be monitored until resolved. All AEs should be recorded in the patient notes, the CRF and on the Adverse Event log in the ISF.

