13. CLINICAL SUPPLIES

The Sponsor will supply all mOm incubators to be used in the clinical study and provide all necessary clinical study related documents such as, CRFs, staff questionnaires, study-related incubator cleaning logs and an Investigator Site File containing all of the other regulatory documents, study logs (screening, enrolment, delegation of authority and AE logs) which need completing, all study manuals, records of training and contracts, plus any other study related documentation.

The hospital will supply access to their standard incubators, routine incubator cleaning materials and standard source documents such as patient charts, monitor downloads, medical records.

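### Hourly pulse, saturation and respiratory readings can show sustained shifts but miss nearly all brief episodes, and no between-incubator comparison of such episodes is planned

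*Combined protocol and SAP*

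**What the plan says.** One secondary objective in section 3.2 is "Comparability to maintain clinical stability by measurement of physiological parameters". Section 4.2.1 serves it with "Pulse rate (Hourly", "Respiratory rate (Hourly" and "Oxygen saturation (Hourly", plus blood pressure at least daily and axillary temperature at the usual care interval. Section 6.2 fixes the timing: "Hourly observations (+/- 15 minutes) will be taken throughout the following 48 hours of incubator care". That is 24 hours in each incubator.

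Section 8 describes the temperature analysis (graphs, variance, and a 95% confidence interval for fluctuation per incubator) and then says "Secondary outcome measures will be presented similarly". It defines no episode count, time outside limits or event comparison for the vital signs.

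Episodes appear elsewhere. The typical adverse events to be recorded under section 7.1 are "skin injury or infection, pressure sores, hyperthermia, hypothermia, apnea and bradycardia", in an open-ended list. Section 13 says that the hospital supplies "standard source documents such as patient charts, monitor downloads, medical records".

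**The concern.** Hourly spot values suit a slowly changing quantity such as temperature. Apnoea, bradycardia and desaturation can be brief, and a brief event seldom coincides with a reading. If the hourly means and variances agree and the report concludes that clinical stability is comparable, a reader may take that to cover brief episodes. The hourly data could not support that conclusion, and the plan names no other analysis that would. At stake is how far the clinical-stability conclusion reaches. The primary temperature endpoint is not affected.

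**Working it through.** **The plan's own figure.** The only sizing figure in section 8 is a half-width of 0.33 degree with 36 babies. It reproduces as 1.96 × SD / √36 = 1.96 × 1.0 / 6 = 0.327, taking an SD of 1.0 (assumed; the plan gives a mean fluctuation of about one degree and no SD). It concerns temperature. No such figure exists for clinical stability.

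**Inputs.** From the documents: one reading per hour, 24 hours per incubator, 36 completed babies, so 36 × 24 = 864 readings per parameter per incubator. If the 19-of-24 completeness rule, written for temperature only, also applied here, the minimum would be 36 × 19 = 684. Assumed, because the documents give neither: episodes of 10 to 60 seconds, falling at random relative to the reading, at 1 to 24 episodes per baby per day.

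**Share of episodes caught.** The chance that an instantaneous hourly reading falls within an episode of d seconds is d / 3600:

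| d (s) | caught |
|---|---|
| 10 | 0.28% |
| 20 | 0.56% |
| 30 | 0.83% |
| 60 | 1.7% |

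If a reading spans a 60-second count, the chance is (d + 60) / 3600, or 1.9% at 10 s and 3.3% at 60 s. Across both cases, about 97% to 99.7% of episodes are missed.

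**Affected readings per incubator.** With k episodes per baby per day, the expected number is 864 × k × d / 86400 = k × d / 100. For d from 10 to 60 s:
- k = 1: 0.1 to 0.6 of 864
- k = 4: 0.4 to 2.4
- k = 24: 2.4 to 14.4

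**Power to show a doubled episode rate** (exact conditional test of two Poisson counts, two-sided 5%, d from 20 to 60 s):
- k = 1: about 0%
- k = 4: 0.3% to 6%
- k = 24: 17% to 54%

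If every episode were counted, 36 babies would give 36 against 72 episodes at k = 1 (power 93%) and 144 against 288 at k = 4 (over 99%). Allowing a fourfold variance inflation for clustering within baby, these fall to about 33% and 93%. This is a ceiling, since no log captures every episode.

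**What the hourly readings can show.** For a paired difference in 24-hour mean pulse, the shift detectable with 80% power is (1.96 + 0.84) × SD / √36. With an assumed SD of the paired difference of 4 to 10 beats/min, that is 1.9 to 4.7 beats/min. Modest sustained shifts are therefore visible.

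**The adverse event route, side by side.**
- 7.1 and 7.4: apnoea and bradycardia are to be recorded over the 48 hours, and all adverse events go in the notes and the log within 10 working days.
- 4.2.4: the adverse event outcome assesses only ADEs and SADEs.
- 7.2: occurrences expected in routine care are not reported unless thought study related. The list is open; its examples do not include apnoea or bradycardia.
- 7.1: desaturation is not named.
- Table 1 in 6.2: the event record asks for incubator alarms and does not mention patient-monitor alarms.

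Episodes may thus be logged, but nothing says that they will be compared between incubators.

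**The case against.** The strongest reply is that the objective is framed through physiological parameters, and 4.2.1 lists levels. Section 7.1 names apnoea and bradycardia as typical adverse events, beside skin injury and pressure sores; it does not define clinical stability by them. Logging them is a requirement under 7.1 and 7.4, and the sponsor tracks it through monitoring. The babies are selected as stable from a cardio-respiratory point of view, so episodes may be rare. Hourly recording already exceeds the three-hourly routine stated in section 5, and there is no margin or test for this outcome.

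Most of that stands, and it rules out two stronger readings. A reader might infer that the incubators will look equally stable whether or not they are. The documents do not support this: paired hourly data can show sustained shifts, and apnoea and bradycardia must be logged. A reader might also infer that the outcome is blind to the very instability it is meant to measure. That depends on a definition of stability by episodes, which the objective does not give.

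Two things are left unanswered. Required logging is not a planned comparison, since 4.2.4 stops at device events. And a low episode rate does not rescue the hourly readings, because they are least informative when episodes are rare.

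A fair caution also applies to the remedy: section 13 names monitor downloads only as an example of a source document. It does not show that they hold continuous trends.

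**Conclusion.** The concern holds in a limited form. The hourly readings support a statement about average level and sustained shifts, not one about brief episodes, and the plan contains no between-incubator comparison of such episodes. The size, about 97% to 99.7% of episodes missed, rests on assumed durations of 10 to 60 seconds and random timing. The power figures also rest on assumed rates of 1 to 24 episodes per baby per day, which may be high for stable babies. Longer episodes would be caught more often. The severity is minor to moderate.

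**What to change.** Amend 4.2.1, 4.2.4 and section 8 as follows.

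1. Keep the hourly values, label them as a description of average level, and present each as the paired within-baby mOm-minus-standard difference with a 95% confidence interval.
2. Tabulate all recorded apnoea, bradycardia and desaturation events by incubator period, whether or not judged device related, and make 4.2.4 and 7.2 consistent with 7.1 on this.
3. Where the monitor downloads contain stored trends, add the percentage of each 24-hour period spent outside a fixed analysis limit, the same in both of a baby's periods, again as a paired difference with a 95% confidence interval. The limit is for analysis only and changes no monitor setting or care.
4. Where they do not, state that the clinical-stability conclusion covers hourly levels only, not brief episodes.

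Items 1, 2 and 4 need amended wording and one table. Item 3 costs data handling and artefact filtering, for example around feeds and handling, and export may be incomplete at some sites. No extra procedure on the baby is involved. Logged counts will still depend on staff who can see which incubator is in use, so the table should be read as descriptive.
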